4.2. Definition of study endpoints

4.2.1. *Primary endpoint*

Relapse free survival (RFS)

RFS is defined as time interval from randomization until relapse of AML or death from any cause, which occurs first. Relapse is defined as any blast appearance in the peripheral blood, in the bone marrow (> 5%) or extra medullary blasts (chloroma). For a patient with no relapse before the end of study follow-up, observation of RFS will be censored at the date of his or her last follow-up examination.

4.2.2. *Secondary endpoint*

Overall survival (OS)

OS is defined as time from randomization to the day of death. For a patient who is not known to have died by the end of follow-up, observation of OS will be censored on the date the patient was last known to be alive.

5. Study design

This is a double blind, placebo-controlled, randomized, multi-centre phase II study. Approximately 10 to 20 centres will participate in this study.

5.1. Study population

200 patients aged ≥ 18 years with Flt3-ITD positive AML, who have undergone allo-SCT

- for chemotherapy-refractory disease,
- or for consolidation in first or second complete remission

will be treated with either placebo (control group) or Sorafenib (verum group) to maintain a CHR and to prevent hematological relapse.

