5.5. Randomization

Randomization will be performed centrally by fax at the

Koordinierungszentrum für klinische Studien (KKS)

Philipps-University Marburg

[name]

[name]

Monday-Thursday 8.00–16.00 h

Friday 08.00–14.00 h

[contact]

[contact]

Randomization will not be possible during public holiday.

The randomization of a registered patient (registration requirements: see 5.4 and flow chart 2.1) can take place, if a registered patient fulfils inclusion/exclusion criteria.

The chance for randomization to the verum group and the placebo group is 1:1.

The KKS reports a package number for the randomized patient back to the centre. The investigator has to note the patient number on the emergency envelope which is already labeled with the corresponding package number, and on the corresponding medication package.

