11.2. Power and Sample Size Calculation

The primary endpoint of the study, relapse-free survival (RFS), is defined as the time interval from randomization until relapse or death from any cause, whichever occurs first. For a patient with none of these events before the end of study follow-up, observation of RFS will be censored at the date of his or her last follow-up examination. It is assumed that the RFS rate after 2 years may be increased from 65% with placebo (Gale et al., Blood 2005; Thiede et al., Blood 2006) to 82.5% with sorafenib, corresponding to a hazard ratio (HR) of 0.45. Comparing the sorafenib with the placebo group by a log-rank test at a two-sided alpha of 5%, 49 observed events are required to obtain a power of 80%. It is important to note that due to a decreasing likelihood of relapses over time, the Kaplan-Meier curve for RFS of Flt3-ITD AML patients after allo-SCT forms a plateau after around 2 years at the above-mentioned values.

Under these assumptions, 184 patients (i.e., 92 per group) are needed in order to observe 49 events after a minimum observation period of 24 months for each patient. The inclusion of a total of 200 patients in the study allows for compensation of a dropout rate of 8%. During the course of the study, it may be decided to adapt the number of included patients. If this is done based on a data inspection (rather than solely on the absolute number of events which occurred so far, irrespective of the study arm), the method for sample-size adaptation in survival trials developed by Schäfer and Müller (Schäfer H, Müller H-H. Modification of the sample size and the schedule of interim analyses in survival trials based on data inspections. Statist Med 2001;20:3741-3751) will be employed which ensures that the type I error risk is not affected. It may also be decided later to add one or more interim analyses using the adaptive method mentioned above, especially if the sample size is increased.

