In order to perform the interim data inspection, the trial biostatistician will receive the data regarding relapse and censoring events together with treatment group membership, that is, in a blinded fashion, without any further variables. The Coordinating Centre for Clinical Studies (KKS) Marburg will provide these data with new random ID numbers, such that the biostatistician can use as little information from the interim inspection as possible at later stages of the analysis, maintaining blinding to the largest possible degree. The results of the interim data inspection (log-rank test statistic, CRP given the test statistic, Kaplan-Meier curves, treatment difference in terms of hazard ratio) as well as recalculated power values assuming the CRP and various effect sizes will be communicated by the biostatistician only to the unblinded contact. The unblinded contact will communicate in an unblinded fashion with the DSMC members. The DSMC will decide about whether and how the design of the remaining part of the trial should be changed, e.g. the sample size reduced in case of an unexpectedly large treatment difference, or whether the trial should be stopped due to futility. This decision will be communicated in written form to the unblinded contact and the Steering Committee. If the design is modified, this will be specified in a further protocol amendment. The details of a design modification will be communicated to as few people involved in the performance of the trial as possible, in order to avoid that study personnel might draw conclusions about the observed treatment difference from the decision regarding the change of trial design.

11.4. *Statistical Analysis Plan*

The primary objective, RFS (as defined above), will be analyzed by means of the Kaplan-Meier method as well as the log-rank test at a two-sided alpha of 0.05 to test for differences between the two study arms. Possible sample size modifications or interim analyses will be performed according to the adaptive method by Schäfer and Müller as described in section 11.2.

Secondary endpoint of the study is overall survival (OS), defined as time from randomization to the day of death; for a patient who is not known to have died by the end of follow-up,

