observation of OS will be censored on the date the patient was last known to be alive. This and other secondary objectives will be analyzed by the Kaplan-Meier method and the log-rank test. Furthermore, RFS and OS will be analyzed by Cox regression in order to account for prognostic factors (Flt3-ITD ratio at diagnosis, treatment with Flt3-inhibitors before allogenic stem cell transplantation, occurrence of chronic GvH). The analysis will be performed according to the intention-to-treat principle.

With regard to safety, numbers of adverse events will be analyzed descriptively as well as in comparison between the two study arms by means of Fisher's exact test.

12. Efficacy

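### Disease status at transplant helps define the population in 5.1 but is missing from the Cox factors in 11.4, so a chance imbalance in it could not be adjusted for

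*Protocol*

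**What the plan says.** Section 5.1 describes the 200 patients by their reason for transplant: "for chemotherapy-refractory disease", "or for consolidation in first or second complete remission". It sets no expected share and no cap for any group.

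Section 5.5 describes central allocation by fax and says "The chance for randomization to the verum group and the placebo group is 1:1". It names no stratification factor.

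Section 11.4 analyses the primary endpoint by the "Kaplan-Meier method as well as the log-rank test at a two-sided alpha of 0.05", with no strata. It then adds Cox regression for RFS and OS to account for three named prognostic factors: "Flt3-ITD ratio at diagnosis, treatment with Flt3-inhibitors before allogenic stem cell transplantation, occurrence of chronic GvH". Nothing in the wording leaves the list open, and disease status at transplant is not on it. None of the secondary objectives in 4.1.2 uses it either.

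Section 11.3 reports 45 patients randomised after 40 months of accrual and says that the sample size could be reduced after the interim data inspection. For that inspection the biostatistician receives events and treatment group without further variables.

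**The concern.** The protocol sorts its patients by a clinical distinction that may well affect relapse, and then does not use it. Details of randomisation and supporting analyses often sit in other documents. Here, though, the protocol itself fixes the list of Cox factors, so an analysis plan that follows it would omit disease status. Adding the factor after results by arm have been seen would look data-driven.

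Sample size is what makes this worth raising. At 200 patients randomisation will usually balance the arms closely. At a number nearer to actual accrual, sizeable differences are fairly common. A reader of the final RFS and OS hazard ratios would then ask whether the arms differed in refractory patients and what the estimate is after allowing for that. The planned model could not answer.

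**Working it through.** **The plan's own figure.** The design hazard ratio is ln(0.825)/ln(0.65) = 0.4466. Events = 4 × (1.960 + 0.842)² / (ln 0.4466)² = 48.3, rounded up to 49 as in 11.2. The sample size reproduces and is not at issue.

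**Inputs**
- From the protocol: 1:1 allocation (5.5); 200 planned patients (11.2); 45 randomised so far (11.3); placebo 2-year RFS of 65% (11.2: "the RFS rate after 2 years may be increased from 65% with placebo").
- Assumed, because the protocol gives no figure: refractory share 30% (range 20-40%); hazard ratio of refractory versus remission 2 to 3.

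**Step 1: how likely is an imbalance?** With X₁ ~ Bin(n₁, p) and X₂ ~ Bin(n₂, p), the exact probability that |X₁/n₁ − X₂/n₂| is at least d:

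| Patients (arms) | Refractory share p | d = 15 points | d = 20 points |
|---|---|---|---|
| 45 (22/23) | 20% | 19% | 9% |
| 45 (22/23) | 30% | 27% | 14% |
| 45 (22/23) | 40% | 34% | 17% |
| 200 (100/100) | 30% | 2.5% | 0.3% |

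Both directions are counted, so the chance of an imbalance favouring sorafenib is about half of each figure.

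**Step 2: what would a 20-point imbalance do with no drug effect?** Let s be the 2-year RFS of remission patients and g the status hazard ratio, so that refractory patients have RFS s^g. Solve 0.7s + 0.3s^g = 0.65 for s. Arm RFS with refractory share q is S(q) = (1 − q)s + q·s^g. The apparent hazard ratio is ln S(0.20) / ln S(0.40).

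| g | s | S(0.20) | S(0.40) | Apparent HR | Inverse |
|---|---|---|---|---|---|
| 2 | 0.712 | 0.671 | 0.629 | 0.86 | 1.16 |
| 2.5 | 0.732 | 0.677 | 0.623 | 0.82 | 1.22 |
| 3 | 0.749 | 0.683 | 0.617 | 0.79 | 1.27 |

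At g = 1.5 the apparent hazard ratio is 0.92.

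**Step 3: is the primary test still valid?** Simulations used exponential times, censoring at 24 months and 30% refractory. Averaged over randomisations at 200 patients, the plain log-rank test rejects a true null in 4.9-5.0% of runs. Its power at a hazard ratio of 0.45 is 81% (g = 2) or 78% (g = 3), against 82% and 81% when stratified by status. Given a 15-point imbalance against sorafenib at 200 patients, the plain test's power falls to 65% (g = 2) or 53% (g = 3), while the stratified test stays near 80%.

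**The case against.** A reader might infer that the trial cannot tell a drug effect from an uneven share of refractory patients. The documents do not support that. Under 1:1 randomisation the unstratified log-rank test already allows for chance imbalance in every covariate. In a simulation with 45 patients and no drug effect, two-sided rejection was 5.0-5.1% for status hazard ratios of 1.5, 2 and 3. With an imbalance of about 20 points favouring sorafenib (4/22 versus 9/23), it was only 5.2%, 5.5% and 6.4%. Rejection in favour of sorafenib was 3.6%, 4.4% and 5.9%, against a nominal 2.5%. An apparent hazard ratio of 0.79-0.86 is also modest beside the design value of 0.45. All of this stands, and it limits the point to interpretation and precision.

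A reader might also infer that randomisation was unstratified. Section 5.5 only describes 1:1 allocation; a randomisation document that is not shown could hold strata. That would not put the factor into the Cox list.

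Three further limits stand:
- No section states that the groups differ in relapse risk after transplant. Every patient must be in marrow-confirmed remission within 14 days before randomisation and start treatment between day 60 and day 100, which may narrow any difference.
- The 45 patients are accrual when 11.3 was written, not a final size. The design may also be left unchanged.
- Which covariates to include is partly a matter of preference, and other candidates such as donor type are unlisted too. Disease status differs in that 5.1 itself uses it to describe the population.

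**Conclusion.** The point holds as an inexpensive improvement to the supporting analysis, not as a flaw in the primary test. The population is described by disease status at transplant, and the Cox list fixed in 11.4 omits it. The harm depends on an imbalance actually arising, plus a small average loss of power. Near 45 patients, 15 points or more is roughly a one-in-four event; at 200 it is rare. The size of any distortion rests on the assumed 30% share and the assumed status hazard ratio of 2 to 3, and it shrinks if either is smaller: at a 10% share, a 20-point difference at 45 patients has a chance of only 2.6%.

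**What to change.** In 11.4, before any further unblinded look, add disease status at transplant to the Cox factors for RFS and OS. Use refractory versus remission, or three levels (refractory, first remission, second remission) if the number of events allows. Report the distribution of this status by arm.

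Confirm that the eCRF captures it. Section 7.1.2 lists medical and cancer history at baseline, but does not name status at transplant as a separate item.

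Keep the log-rank test as primary. A log-rank test stratified by status can be added as a prespecified sensitivity analysis. Adding the covariate does not change the primary test, so that test remains as exposed to imbalance as before; what improves is the adjusted estimate and the reader's ability to judge the result.

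The cost is a line or two of text and one or two extra model parameters. Sample size, alpha and the adaptive method are unchanged.

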5.2. Inclusion criteria

- Written informed consent
- Age ≥ 18 y.
- ECOG performance ≤ 1
- FLT3-ITD-positive AML
- Complete hematological remission (CHR) after allo-SCT
- CHR must be confirmed by bone marrow analysis within 14 days before randomization (CHR criteria are: $\leq 5\%$ marrow blasts, no peripheral blasts, blood platelet count $> 100/\text{nl}$, WBC count $> 3 \text{ G/L}$, ANC $> 1 \text{ G/l}$).
- Allo-SCT with a HLA-identical allo-family donor (FAM) or a matched unrelated donor (MUD) with up to 1 antigen mismatch acceptable (9/10)
- Time point of study treatment start of patients in CHR: between d+60 up to d+100 after allo-SCT
- Adequate organ function:

-
- Serum creatinine ≤ 1.5 x upper normal value
 - ALT, AST, AP ≤ 2.5 x upper normal value
 - Total bilirubin ≤ 1.5 x upper limit of normal
 - PT-INR/PTT ≤ 1.5 x upper limit of normal
 - Patients who are being therapeutically anticoagulated with an agent such as Coumadin or Heparin will be allowed to participate provided that no prior evidence of underlying abnormality in these parameters exists)
 - Negative serum pregnancy test within seven days prior to first dose in women of child-bearing potential (WOCBP)
 - WOCBP must use a double barrier method of contraception during the study and for 3 months following the last dose of study drug. WOCBP are defined as sexually mature women who have not undergone a hysterectomy or surgical sterilization or who have not been naturally postmenopausal for at least 12 consecutive months (i.e., who has had menses any time in the preceding 12 consecutive months).
 - Male subjects whose sexual partners are WOCBP must use a double barrier method of contraception, one of which includes a condom, during the study and for 3 months after the end of treatment.

5.3. Exclusion criteria

- Any severe concomitant conditions which make it undesirable for the patient to participate in the study or which could jeopardize compliance with the protocol (such as substance abuse, uncontrolled infection, known HIV, HBV, HCV infection).
- Psychiatric disorder that interferes with ability to understand the study and give informed consent, and/or impacts study participation or follow-up.
- Cardiac disease: heart failure NYHA III/IV, unstable coronary artery disease (MI more than 6 months prior to study entry is permitted), serious cardiac ventricular arrhythmias requiring anti-arrhythmic therapy (beta-blockers or digoxin are permitted).
- Resting blood pressure consistently higher than systolic 150 mmHg and/or diastolic 90 mmHg despite antihypertensive therapy
- Patients undergoing renal dialysis
- Evidence or history of severe non-leukemia associated bleeding diathesis or coagulopathy
- Patients with uncontrolled seizure disorder despite medication
- History of organ allograft (except for allogenic SCTX)

- Patients with major surgery, open biopsy, or significant traumatic injury within 4 weeks prior to start of first dose of study drug
- Serious non-healing wound, ulcer or bone fracture
- Known Flt3-kinase inhibitor resistance
- Previous Sorafenib therapy
- Active (uncontrolled) graft versus host disease GvHD (> grade I) at time of randomization despite the use of adequate therapeutic measures
- Investigational drug therapy outside of this trial during or within 4 weeks of study entry
- Pregnancy or breast feeding
- Allergy to study medication or compositions of excipients in study medication
- Secondary allo-SCT
- Previous or concurrent cancer curatively treated ≤ 3 years prior to study entry

5.4. Registration

Registration of screened patients will be performed before randomization (flow chart 2.1) in the central database (e-CRF) for patient documentation (see chapter 13.3). This registration is a mandatory condition for randomization. The Patient-ID is combined from the site number (2-digit, starting with 01) and a sequencing number of the patients starting with 01 for each site. The investigator enters at registration only the sequencing number. This unique Patient-ID is used for all documentation on e-CRF and DCF.

5.5. Randomization

Randomization will be performed centrally by fax at the

Koordinierungszentrum für klinische Studien (KKS)

Philipps-University Marburg

[name]

[name]

Monday-Thursday 8.00–16.00 h

Friday 08.00–14.00 h

[contact]

[contact]

Randomization will not be possible during public holiday.

The randomization of a registered patient (registration requirements: see 5.4 and flow chart 2.1) can take place, if a registered patient fulfils inclusion/exclusion criteria.

The chance for randomization to the verum group and the placebo group is 1:1.

The KKS reports a package number for the randomized patient back to the centre. The investigator has to note the patient number on the emergency envelope which is already labeled with the corresponding package number, and on the corresponding medication package.

5.6. Blinding

Both, subjects and the investigators will be blinded to treatment assignment.

Before inclusion of the first patient, each study centre will obtain sufficient study medication for the first six patients from the pharmacy of the University Dresden. Medication for any patient will be labelled by the Pharmacy Dresden with a package number. The investigator at the centre will have to note the patient number on the designated medication package (s.5.5) after randomization.

5.7. Unblinding

Un-blinding may occur for emergency purposes only. Investigators should note that the occurrence of a Serious Adverse Event should not routinely precipitate the immediate un-blinding of the label. In case an adverse event makes it necessary for the treating physician to unblind the study medication, the envelope can be opened - if possible, after prior contact with the study coordinator in Marburg. If this is not feasible, the study coordinator in Marburg must be contacted within 24 hours after un-blinding. The date and the event making it necessary to un-blind the treatment randomization have to be documented in the patient files and in the CRF, on a specific sheet.

After the trial will be ended, envelopes have to be returned to the sponsor.

5.8. Withdrawal of patients from study treatment

In accordance with the Declaration of Helsinki, each subject may voluntarily withdraw from the study at any time without giving reasons for this decision. The decision to withdraw from the study treatment must be without any prejudice for the patient.

Study treatment of a patient **may** also be terminated by the investigator for one of the following reasons:

- Severe (S)AE which make it necessary to stop study treatment
- Abnormal laboratory value(s) which make it necessary to stop study treatment
- Abnormal test procedure result(s) which make it necessary to stop study treatment
- Non-compliance with the study protocol
- Physicians decision

Study treatment **has to be** terminated for one of the following reasons:

- Subject withdrew consent
- Relapse of disease
- Pregnancy

If the investigator withdrew the patient prematurely, he has to inform the patient about his decision and has to record the primary reason for the withdrawal in the patient's medical record and on the end of treatment CRF. Safety assessments will be performed at the date of discontinuation and approximately one month after last dose of study drug. Final study evaluations will be done according to the evaluation plan outlined in table 6.

If the patient caused the premature withdrawal, all data before termination may be used for final analysis. After termination they will be followed until end of study or death. Safety assessments will be performed at the date of discontinuation and approximately one month after last dose of study drug. Off study evaluations will be done according to the evaluation plan outlined in table 6.

5.9. Premature Discontinuation of the study

5.9.1. Single centre

The sponsor, together with the PI, the Competent Authority and the ethical committee (EC) have the right to discontinue this study at any time for reasonable medical or administrative reasons in any single centre. Possible reasons for termination of the study could be but are not limited to:

- Unsatisfactory enrolment with respect to quantity or quality
- Inaccurate or incomplete data collection

-
- Unexpected accumulation of SAE/AE
 - Falsification of records
 - Major failure to adhere to the study protocol

5.9.2. Study as a whole

The sponsor together with the PI, the Competent Authority and the EC have the right to terminate this clinical study as a whole at any time for reasonable medical or administrative reasons. Any possible premature discontinuation would be documented adequately with reasons being stated, and information would have to be issued according to local requirements (e.g., IRB/EC, regulatory authorities).

6. Study medication

6.1. Sorafenib and Placebo - general aspects

Sorafenib (Nexavar®) is an oral cytostatic Raf-kinase inhibitor, PDGFR inhibitor, VEGFR-2 (KDR) inhibitor and Flt3 inhibitor. The drug product for supply of clinical trials is a 200mg-coated tablet (calculated as free base Sorafenib). The formulation is presented as an immediate release (IR) dosage form.

For blinding purpose in this controlled clinical trial, corresponding placebo tablets are available.

For more details please refer to the Summary of Product Characteristics (SmPC) of Sorafenib (Nexavar®) in the Investigator's Folder.

